10.3. Statistical Analyses

10.3.1. General Statistical Considerations

Statistical analysis of this study will be the responsibility of Lilly or its designee. Any change to the data analysis methods described in the protocol will require an amendment only if it changes a principal feature of the protocol. Any other change to the data analysis methods described in the protocol, and the justification for making the change, will be described in the statistical analysis plan (SAP) or the clinical study report (CSR). Additional exploratory analyses of data will be conducted, as deemed appropriate.

Given the nature of this pragmatic study, both efficacy and safety analyses will be performed on randomized patients. As sensitivity analyses, certain efficacy analyses may be repeated by censoring all efficacy data after patients changed the randomized treatment regimen.

All tests of treatment effects will be conducted at a 2-sided alpha level of 0.05, unless otherwise stated.

The baseline value for measurements will be defined as the last non-missing observation on or before the randomization visit. If no data are available, the baseline value will be treated as missing. The Week 24 value for measurements will be the last non-missing post-baseline observation up to 24 weeks, and the Week 48 value for measurements will be the last non-missing post-baseline observation up to 48 weeks.

For continuous measures, summary statistics will include at least the number of patients with data, mean, SD, median, minimum, and maximum. For categorical measures, summary statistics will include at least the number of patients with data, frequency counts, and percentages. For comparisons based on analysis models, the differences will be reported using LS means, along with 95% CIs and p-value. Sometimes, comparison on the summary statistics may be performed and p-values be provided, and such p-values should be viewed as a descriptive measure only. Unless specified otherwise, a two-sample t-test will be used for continuous measurements and Fisher's exact test will be used for categorical measurements.

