8.2.2. Secondary Analyses

Missing efficacy values which are HbA1c, FPG, FSBG-based FBG, PPG, BG excursion daily insulin, body weight, SEITQ score will do LOCF. Those missing values will be the last non-missing post-baseline observation up to date of missing values of measurement.

All secondary efficacy endpoints will be listed separately for each subject at each planned visit.

1. For change from baseline in HbA1c at Week 48, the analyses model will be similar to the primary analyses model, and the sensitivity analyses will also be performed.

Also, a mixed-model repeated measures (MMRM) model will be employed to analyze the HbA1c change from baseline at Week 24 and Week 48. This MMRM model will have all post-baseline HbA1c as responses, baseline HbA1c as a continuous covariate, treatment group, Visits (Week 24 or Visit 48), and treatment by visit interaction as fixed effects and patient as a random effect. An unstructured covariance structure will be used to model the correlation within subjects. In case of failure of convergence using unstructured covariance structure, the first-order autoregressive [AR(1)] covariance structure will be used. Missing data will be assumed to be missing at random and therefore maintained as missing. The difference between each of treatment will be assessed by the least-squares means (LSM) difference at Week 24 and Week 48 (alpha=0.05, 2-sided).

A plot of least-squares means for change from baseline by visit for each treatment will be used to display the results of this endpoint.

As sensitivity analyses, the endpoint analyses will be repeated by censoring all efficacy data after patients changed the randomized treatment regimen at Week 48, Ancova analyses for row data and LOCF data at Week 48 separately.

2. For change from baseline in venous FPG, FSBG-based FBG, PPG, BG excursion and bodyweight at Week 24 and Week 48, the analyses will be done similarly to the primary analyses model (ANCOVA for Week 24 and Week 48, and MMRM for Week 24 and Week 48), except for comparison will be based on the treatment contrast p-value from the corresponding analyses model. The sensitivity analyses will also be performed.

Plots of least-squares means for change from baseline by visit for each treatment will be used to display the results of endpoints.

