As sensitivity analyses, the endpoint analyses will be repeated by censoring all efficacy data after patients changed the randomized treatment regimen at Week 24 and Week 48, Ancova analyses for row data and LOCF data at Week 24 and Week 48 separately.

3. For percentages of patients reaching treatment goals (<7%) at Week 24 and Week 48, no missing data will be imputed. Count and percentages of patients reaching treatment goals will be summarized (when calculating percentages, the denominator will be the patients with non-missing HbA1c data at Week 24 or Week 48), and also be analyzed by a logistic regression model, with logit link function, treatment as fixed effect and baseline HbA1c as continuous covariate. Adjusted odds ratio, 95% CI and P-value will be presented. Related plot will be reported.

Plots of percentages of patients reaching treatment goals by visit for each treatment will be used to display the results of endpoints.

As sensitivity analyses, the endpoint analyses will be repeated by censoring all efficacy data after patients changed the randomized treatment regimen at Week 24 and Week 48, Ancova analyses for row data and LOCF data at Week 24 and Week 48 separately.

4. Same analyses strategy (refer to above 3) will be used for the composite endpoint of patients reaching treatment goals (<7%) and did not switch from or discontinue study treatment, and did not take rescue medication. Those patients should be without switching or discontinuing study insulin, and without using rescue therapy which will be determined by the investigator following usual standard of care between insulin analog mid mixture BID and basal insulin analog QD treatments.
5. Insulin dose at each visit will be descriptively summarized by treatment groups by total daily dose (IU and IU/kg). The descriptive statistics (n, mean, median, standard deviation, minimum, and maximum) and P-value of a two-sample t-test will be reported.
6. Time to insulin treatment change will be compared between treatment arms by a log rank test. Table and related plot will be reported. Patients who did not have any insulin treatment change up to Week 48 (or up to early discontinuation) will be considered as censored at Week 48 (or time of early discontinuation) with no event. Time to insulin treatment change: Defined as time to any of: insulin treatment

discontinuation, switch, intensification or reduction in frequency. ((date of event/censored - (date of first dose of study drug) + 1.)

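### SAP 8.2.2 makes LOCF the general rule for eight measures while its items 3 and 4, SAP 7.1 and Appendix 1 point to observed values, so the dataset for the main Week 48 ANCOVA is undefined

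*SAP*

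**What the plan says.** **General rule.** SAP 8.2.2 begins with a list of eight measures (HbA1c, venous FPG, finger-stick FBG, PPG, excursion, insulin dose, body weight and SEITQ) that ends: "SEITQ score will do LOCF. Those missing values will be the last non-missing post-baseline observation up to date of missing values of measurement".

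**Responder endpoints.** Item 3 of the same section says: "For percentages of patients reaching treatment goals (<7%) at Week 24 and Week 48, no missing data will be imputed". For the percentages, "the denominator will be the patients with non-missing HbA1c data at Week 24 or Week 48". Item 4 extends this: "Same analyses strategy (refer to above 3) will be used for the composite endpoint". Yet item 3's sensitivity paragraph asks for ANCOVA on raw data and on LOCF data, although the endpoint is binary and its main model is logistic regression.

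**Week 48 HbA1c and the other continuous endpoints.** Item 1 describes the Week 48 HbA1c ANCOVA only as similar to the primary model. It adds an MMRM with its own rule: "Missing data will be assumed to be missing at random and therefore maintained as missing". Item 2 plans both ANCOVA and MMRM for FPG, FBG, PPG, excursion and body weight, and bases the comparison on the p-value of whichever model corresponds. In items 1 and 2, raw and LOCF ANCOVA are listed separately as sensitivity analyses.

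**Which record is the Week 48 value.** Protocol 10.3.1 says "the Week 48 value for measurements will be the last non-missing post-baseline observation up to 48 weeks". SAP 7.1 uses the last record inside each Appendix 1 window, and the Week 48 window there runs from after Visit 4 to Visit 6.

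**Lead analysis.** Protocol 10.3.3.2 states that the MMRM treatment contrast at Week 48 serves for inference on HbA1c. SAP 8.2.2 does not repeat this.

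**The concern.** Two analysts could both follow the SAP and build different Week 48 datasets. One would carry Week 24 HbA1c forward under the opening sentence. The other would use the Appendix 1 window and leave the value missing. The reference to the primary model does not settle it: SAP 8.2.1 gives as its reason for not imputing that HbA1c has a single post-baseline measurement by Week 24, and that reason does not apply at Week 48.

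Under LOCF, a Week 48 HbA1c or FPG result includes values that are not 48-week values. The Schedule of Activities has these tests after baseline only at Weeks 24 and 48 and at early termination, so nothing else can be carried. LOCF assumes no change after the last visit, and it counts carried values as if they were measured, which makes the confidence interval too narrow. For the item 2 endpoints, it is also unclear whether ANCOVA or MMRM supplies the deciding p-value.

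**Working it through.** **1. The plan's own figures.** Inputs from SAP 5 and Protocol 10.1: SD 1.5, margin 0.4, 332 evaluable per arm, 20% dropout.

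- SE = 1.5 × √(2/332) = 0.1164; 95% half-width = 1.96 × 0.1164 = 0.228.
- The classification fails to conclude only if L ≤ −0.4 and U ≥ 0.4 together, which needs a half-width of at least 0.4. At 0.228 the probability of a conclusion is practically 1, in line with the stated figure of more than 99%.
- 332 / 0.80 = 415 per arm; 2 × 332 = 664. Both agree with the plan.

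These figures concern Week 24. They are used below only for the SD and the starting number.

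**2. One patient under each rule.** Take a patient with HbA1c at Visit 4 and none later.

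| Rule | Week 48 HbA1c |
|---|---|
| SAP 8.2.2, opening | Week 24 value |
| Protocol 10.3.1 | Week 24 value |
| SAP 7.1 with Appendix 1 | missing |
| SAP 8.2.2 items 3 and 4 | missing, outside the denominator |
| SAP 8.2.2 item 1, MMRM | missing; Week 24 value used as Week 24 |

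The first two rows conflict with the third and fourth. The last row is specific to one model.

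**3. Number analysed and precision at Week 48.** The documents give no loss rate between Weeks 24 and 48, so 5% to 20% is assumed. With k = 332 × (1 − loss), the half-width is 1.96 × 1.5 × √(2/k).

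| Assumed loss | Observed N | LOCF N | Difference | Half-width, observed | Half-width, LOCF |
|---|---|---|---|---|---|
| 5% | 631 | 664 | 33 | 0.234 | 0.228 |
| 10% | 598 | 664 | 66 | 0.241 | 0.228 |
| 15% | 564 | 664 | 100 | 0.248 | 0.228 |
| 20% | 531 | 664 | 133 | 0.255 | 0.228 |

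**4. Shift in the HbA1c difference from LOCF.** As an approximation, shift = (share carried in one arm − share carried in the other) × mean change after Week 24.

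- 10-point imbalance, 0.5 change: 0.10 × 0.5 = 0.05.
- 15-point imbalance, 0.3 change: 0.15 × 0.3 = 0.045.
- Equal loss, no true difference: 0.
- Equal loss of 5%, 10% or 20%, with a true difference of 0 at Week 24 and 0.30 at Week 48: LOCF estimates 0.30 × (1 − loss) = 0.285, 0.27 or 0.24.

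**5. Simulation of the three approaches.** Assumptions: 332 per arm with Week 24 values, SD 1.5, within-patient correlation 0.6, true Week 48 difference 0, and missingness that depends on the Week 24 value. No baseline covariate was included. The last column is a likelihood-type estimate equivalent to the MMRM in this two-visit setting. Loss rates are nominal.

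| Loss by arm | Rise from Week 24 to 48 | Observed | LOCF | MMRM-type |
|---|---|---|---|---|
| 10% / 10% | 0.3 | −0.001 | −0.001 | −0.002 |
| 10% / 20% | 0.3 | 0.040 | 0.009 | −0.002 |
| 5% / 20% | 0.3 | 0.068 | 0.016 | 0.002 |
| 5% / 20% | 0.5 | 0.062 | 0.042 | −0.003 |

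Observed and LOCF estimates differ by at most 0.068 − 0.016 = 0.052 here. Step 4 gives at most 0.30 − 0.24 = 0.06.

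**6. Responders.** Assume a 50% rate in observed patients and a 30% Week 24 rate in those missing Week 48. The LOCF rate is 0.5 × (1 − loss) + 0.3 × loss. With 5% versus 20% loss this is 0.49 versus 0.46, a difference of 3 points where the observed data show none. With equal loss the difference is 0.

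**The case against.** The strongest reply is that the text already settles much of this.

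- **MMRM.** A reader might infer that leaving data missing in the MMRM contradicts LOCF. It does not. The sentence governs one model, and an MMRM on observed data can stand beside a LOCF ANCOVA.
- **Lead analysis.** A reader might infer that no lead analysis exists for Week 48 HbA1c. Protocol 10.3.3.2 names the MMRM contrast. What stands is that the SAP omits this and that item 2 leaves the choice of model open.
- **Responders.** A reader might infer that two denominators are equally planned for the main result. Items 3 and 4 and Protocol 10.3.3.2 state a specific rule, which naturally overrides a general opening sentence. What stands is the literal conflict, and that item 3 itself brings LOCF and ANCOVA back in its sensitivity paragraph.
- **Disclosure.** Raw and LOCF ANCOVA are both listed as sensitivity analyses for items 1 to 3, so both would be reported. That limits selective choice, but it does not say which dataset the main ANCOVA uses.
- **Scope.** LOCF covers eight named measures. It does not reach time to insulin treatment change or hypoglycemia.
- **Alternatives.** Observed-data analysis is not unbiased either. In the unequal-loss scenarios it was further off than LOCF (0.068 against 0.016). This stands, and it is a reason to lead with the MMRM and not with observed-data ANCOVA.

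**Conclusion.** The concern holds as a conflict of wording with a small numerical effect. The general LOCF sentence contradicts the rule for the HbA1c <7% endpoints. Protocol 10.3.1 contradicts SAP 7.1 and Appendix 1 on whether a Week 24 value may count as Week 48. The main Week 48 ANCOVA dataset is not identified.

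Under assumed losses of 5% to 20% after Week 24, the choice affects about 33 to 133 of 664 patients, the HbA1c difference by about 0 to 0.06 percentage points, and the responder difference by 0 to 3 points. The loss rates, arm imbalance, later change in HbA1c and responder rates are all assumptions. The shifts are small against the 0.4 margin and grow with unequal loss or with change after Week 24.

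A reader might infer that the primary conclusion is at risk. The documents do not support that: SAP 8.2.1 imputes nothing at Week 24, and neither the primary analysis nor the sample size depends on the conflict in SAP 8.2.2. For HbA1c the issue is essentially confined to Week 48. Body weight and insulin dose are also recorded at Weeks 4 and 12, so LOCF could affect their Week 24 values as well.

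**What to change.** 1. Remove the general LOCF sentence from SAP 8.2.2. Keep LOCF, if at all, only as a labelled sensitivity analysis; dropping it altogether is a matter of preference.
2. Align Protocol 10.3.1 with SAP 7.1 and Appendix 1, so that the Week 48 value comes from the Week 48 window. State in the same place how to allot early-termination values, since an early leaver has no Visit 6 date. Do the same for Week 24 HbA1c samples drawn after Visit 4, because the Schedule of Activities allows 4 weeks either side of the visit.
3. Restore in the SAP the MMRM contrast as lead for HbA1c at Week 48. Name it as lead for the item 2 endpoints (FPG, FBG, PPG, excursion, body weight), with observed-data ANCOVA as support.
4. Keep observed data only for the main responder analyses. Use logistic regression, not ANCOVA, for their sensitivity analyses.
5. Leave insulin dose and SEITQ with the summaries already planned, on observed data. No MMRM needs to be added for them.

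The cost is a short wording change in both documents and a smaller Week 48 ANCOVA set: 33 to 66 fewer of 664 patients if 5% to 10% are lost after Week 24 (an assumption). No new data are needed. The change should be made before Week 48 data are analysed.

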10.3.3.2. Secondary Analyses

For change from baseline in HbA1c at Week 48, the analyses model will be similar to the primary analyses model, and the sensitivity analyses will also be performed. Also, a mixed-model repeated measures (MMRM) model will be employed to analyze the HbA1c change from baseline at Week 48. This MMRM model will have all post-baseline HbA1c as responses, baseline HbA1c as a continuous covariate, treatment group, Visit (Week 24 or Visit 48), and treatment by visit interaction as fixed effects and patient as a random effect. Treatment contrast at Week 48 will be used for making the inference.

For change from baseline in venous FPG, FSBG-based FBG, PPG, BG excursion and bodyweight at Week 24 and Week 48, the analyses will be done similarly to the primary analyses model (ANCOVA for Week 24 and Week 48, and MMRM for Week 48), except for the comparison will be based on the treatment contrast p-value from the corresponding analyses model.

For percentages of patients reaching treatment goals ($<7\%$) at Week 24 and Week 48, no missing data will be imputed. Count and percentages of patients reaching treatment goals will be summarized (when calculating percentages, the denominator will be the patients with non-missing HbA1c data at Week 24 or Week 48), and also be analyzed by a logistic regression model, with logit link function, treatment as fixed effect and baseline HbA1c as continuous covariate. Same analyses strategy will be used for the composite endpoint of patients reaching treatment goals ($<7\%$) and did not switch from or discontinue study treatment, and did not take rescue medication.

Insulin dose at each visit will be descriptively summarized by treatment groups by total daily dose (IU and IU/kg).

Time to insulin treatment change (as defined in Section 9.9.1) will be compared between treatment arms by a log rank test at Week 48. Patients who did not have any insulin treatment change up to Week 48 (or up to early discontinuation) will be considered as censored at Week 48 (or time of early discontinuation) with no event.

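### Read literally, the two-visit MMRM is over-parameterised; this leaves the treatment contrast unchanged but can trigger an AR(1) fallback that assumes equal Week 24 and Week 48 variances

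*SAP*

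**What the plan says.** SAP 8.2.2 item 1 plans an MMRM for change in HbA1c. Its fixed terms include "Visits (Week 24 or Visit 48), and treatment by visit interaction as fixed effects", so there are two repeated measurements per patient. The within-patient part is described as "patient as a random effect. An unstructured covariance structure will be used to model the correlation within subjects". The fallback follows: "In case of failure of convergence using unstructured covariance structure, the first-order autoregressive [AR(1)] covariance structure will be used". Treatments are compared by the "least-squares means (LSM) difference at Week 24 and Week 48 (alpha=0.05, 2-sided").

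Item 2 carries the approach over to venous FPG, FSBG-based FBG, PPG, BG excursion and body weight ("ANCOVA for Week 24 and Week 48, and MMRM for Week 24 and Week 48"), and bases the comparison on the p-value of the treatment contrast from the corresponding model.

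Protocol 10.3.3.2 describes the HbA1c model with "treatment by visit interaction as fixed effects and patient as a random effect" and names no covariance structure. It adds: "Treatment contrast at Week 48 will be used for making the inference".

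The primary Week 24 analysis (SAP 8.2.1) is an ANCOVA and does not use this model.

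**The concern.** A random intercept and an unstructured residual covariance both describe the correlation between a patient's two values. With only two visits the unstructured matrix already describes it fully, so the intercept variance has nothing left to estimate. Software fitting both will meet a flat direction in the likelihood and may report a non-positive-definite Hessian or fail to converge. The SAP does not say which of these counts as a convergence failure, so the specification can trigger its own fallback for a reason unrelated to the data.

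The fallback then gives up the useful property of the unstructured matrix, which is a separate variance at each visit. What is at stake is the calibration of the MMRM confidence intervals and p-values for Week 48 HbA1c and the item 2 endpoints.

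**Working it through.** **Inputs.** Two visits, patient random effect, unstructured covariance and AR(1) fallback: SAP 8.2.2. SD of 1.5% for Week 24 HbA1c change and 332 evaluable per arm: SAP 5. Not in the documents, so assumed: a Week 48 SD, a within-patient correlation (0.5 in the simulation) and missingness at Week 48 (12% of Week 24 patients, completely at random).

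**The plan's own figures.** The documents state no figure for the MMRM. The sample-size figures in SAP 5 reproduce: SE = 1.5 × sqrt(2/332) = 0.116, 95% half-width 1.96 × 0.116 = 0.228, and 332/0.8 = 415 randomized per arm. The full interval width of 0.456 is below 0.8, so the chance of some conclusion is effectively 1, in line with the stated figure above 99%. None of this depends on the MMRM.

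**Step 1: parameter count.** The covariance of (Week 24, Week 48) has three distinct elements: two variances and one covariance.

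| Structure | Parameters | Rank | Identified |
|---|---|---|---|
| Unstructured alone | 3 | 3 | yes |
| Random intercept + unstructured | 4 | 3 | no |
| AR(1) alone | 2 | 2 | yes |
| Random intercept + AR(1) | 3 | 2 | no |
| Random intercept + independent residual (protocol, read literally) | 2 | 2 | yes, equal variances |

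The random intercept adds the same constant to all three elements, which the unstructured matrix can absorb exactly.

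**Step 2: effect on the estimate.** In one simulated data set with 332 per arm, the REML fit was run with the unstructured matrix alone, and then with a random intercept added whose variance was fixed at 0.2, 0.5 and 0.9. All four fits gave a Week 48 contrast of 0.2768, SE 0.1419 and log-likelihood -1173.684. Only the split of the variance components is undetermined.

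**Step 3: effect of the fallback.** On two visits AR(1) has one variance and one correlation, as compound symmetry has. With balanced data the common SD is s_p = sqrt((s24² + s48²)/2), and the actual two-sided error at visit v is 2 × [1 − Φ(1.96 × s_p/s_v)].

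- SDs 1.4 and 1.6: s_p = sqrt((1.96 + 2.56)/2) = 1.503. Week 24: 1.96 × 1.503/1.4 = 2.105, error 3.5%. Week 48: 1.96 × 1.503/1.6 = 1.842, error 6.6%.
- SDs 1.3 and 1.7: s_p = sqrt((1.69 + 2.89)/2) = 1.513. Week 24: 2.282, error 2.3%. Week 48: 1.745, error 8.1%.
- Equal SDs: s_p/s_v = 1, error 5.0% at both visits.

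Over a range of r = SD at Week 48 / SD at Week 24, the Week 48 SE ratio (AR(1) to unstructured) is sqrt((1 + r²)/2)/r:

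| r | Week 48 SE ratio | Week 48 actual error | Week 24 SE ratio |
|---|---|---|---|
| 0.8 | 1.13 | 2.7% | 0.91 |
| 0.9 | 1.06 | 3.8% | 0.95 |
| 1.0 | 1.00 | 5.0% | 1.00 |
| 1.1 | 0.96 | 6.1% | 1.05 |
| 1.2 | 0.92 | 7.1% | 1.10 |
| 1.3 | 0.89 | 8.0% | 1.16 |

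Simulation with 12% missing at Week 48 (500 runs per r) gave Week 48 SE ratios within 0.01 of these. The unstructured model alone held its Week 48 error at 4.0% to 5.4%.

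**The case against.** The strongest reply is that the sentence is loosely worded and the intended model is standard: patient is the subject, and the unstructured matrix is how that subject's correlation is modelled. The two statements stand side by side, and the fallback clause replaces only the covariance structure. On that reading nothing is over-parameterised. This is plausible and cannot be excluded, but it is a reason to correct the text, since a programmer following it literally would fit both terms.

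Three further objections stand.

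- Harm needs two events together: the fallback must be invoked and the visit SDs must differ. The unstructured model alone fitted without difficulty on simulated data of this size and should rarely fail. How often the redundancy would cause a failure depends on the software.
- The SDs behind the error rates are assumed, and the direction is unknown. If Week 24 were the more variable visit, the Week 48 test would be conservative.
- Exposure is limited. Week 48 HbA1c and every item 2 endpoint also have by-visit ANCOVAs, which make no assumption of equal variance across visits.

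A reader might infer that the treatment effect cannot be estimated, or that the MMRM standard errors will be wrong whatever happens. Neither follows: Step 2 shows the contrast and SE unchanged, and the error in Step 3 is zero when the SDs are equal. Nor does the protocol share the identifiability problem. A patient random effect alone is identified, although taken literally it too implies equal variances.

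**Conclusion.** The point holds in a limited form. Taken literally, SAP 8.2.2 item 1 puts four covariance parameters on three elements. This is harmless to the contrast and its SE but gives a singular Hessian, and so a needless route to AR(1). If AR(1) is then used and the visit SDs differ, a nominal 5% test at Week 48 has an actual error between 2.7% and 8.0% for SD ratios of 0.8 to 1.3, with Week 24 erring the other way. Those figures rest on assumed SDs and on balanced or nearly balanced data.

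Protocol 10.3.3.2 and the SAP also lead to different models if each is followed literally. Only the MMRMs of secondary endpoints are affected; the primary ANCOVA and the sample size are not. The change is worth making because it is cheap and specific, not because a result is known to be wrong.

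**What to change.** In SAP 8.2.2 item 1, delete the patient random effect. State that patient is the repeated-measures subject, with an unstructured 2x2 residual covariance across Week 24 and Week 48. Bring the wording of protocol 10.3.3.2 into line.

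Replace the AR(1) fallback with one that does not rely on equal variances: robust (sandwich) standard errors, or the by-visit ANCOVA that the plan already includes. A heterogeneous AR(1) or heterogeneous compound-symmetry structure would not serve, because on two visits it is the unstructured model again.

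The cost is a sentence or two in the SAP and the matching protocol wording, with no change to data collection or sample size. Protocol 10.3.1 requires an amendment only for a change to a principal feature, and otherwise lets changes to analysis methods be described in the SAP. If this is not regarded as a principal feature, the SAP edit can come first and the protocol text can follow at its next revision.

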9. To compare time to insulin treatment change between insulin analog mid mixture BID and basal insulin analog QD treatments	
9. Time to insulin treatment change: Defined as time to any of: insulin treatment discontinuation, switch, intensification or reduction in frequency
 
Discontinuation: Defined as stopping insulin treatment for 30 days or more.
 
Switch: Defined as stop the initial insulin therapy and started another insulin therapy of different class.
 
Intensification: Defined as any of the following: adding meal time insulin in basal insulin analog QD group; changing from BID to TID in insulin analog mid mixture BID group
 
Reduction in frequency: Defined as any of the following: changing from BID to QD; changing from TID to BID or QD

10. To compare the proportion of patients who achieve the HbA1c <7% without switching and discontinuing study insulin, and without using rescue therapy between insulin analog mid mixture BID and basal insulin analog QD treatments	10. Proportion of patients who achieve the HbA1c <7% without switching and discontinuing study insulin, and without using rescue therapy
11. To compare the patients-reported self-efficacy related to insulin therapy as assessed using SEITQ between insulin analog mid mixture BID and basal insulin analog QD treatments	11. The change in SEITQ score form baseline at 48 weeks

Tertiary/Exploratory	

12. To compare the insulin treatment pattern for
 
 • discontinuation • switch • intensification • reduction in frequency 
between insulin analog mid mixture BID and basal insulin analog QD treatments
	
12. Time to insulin discontinuation, switch, intensification or reduction in frequency
 
Proportion of patients who experience insulin discontinuation, switch, intensification or reduction in frequency during 48 weeks

13. To compare healthcare resource utilization (all-cause and T2DM-related; inpatient, outpatient and ER) between insulin analog mid mixture BID and basal insulin analog QD treatments
	
13. Healthcare resource utilization (all-cause and T2DM-related; inpatient, outpatient and ER) during 48 weeks

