8.3.1. Adherence and Insulin Treatment Pattern

For these measurements which are the insulin treatment pattern for insulin discontinuation, switch, intensification or reduction in frequency, summary statistics will be provided, and comparison will be performed by appropriate general test (Fisher's exact test). Proportion of patients who experience insulin discontinuation, switch, intensification or reduction in frequency during 48 weeks and P value should be in summary statistics.

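### Endpoint 10 (HbA1c below 7% without switch, discontinuation or rescue) drops known failures who have no HbA1c, and in the SAP inherits a censoring analysis and an ANCOVA that do not fit a yes/no composite

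*SAP*

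**What the plan says.** SAP section 3 defines endpoint 10 as the "proportion of patients who achieve the HbA1c <7% without switching and discontinuing study insulin, and without using rescue therapy". Its analysis is set by cross-reference. SAP 8.2.2 item 4 says "Same analyses strategy (refer to above 3) will be used for the composite endpoint of patients reaching treatment goals", and Protocol 10.3.3.2 says "Same analyses strategy will be used for the composite endpoint of patients reaching treatment goals".

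The strategy referred to is that of the plain HbA1c below 7% endpoint:

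- **Missing data and denominator (both documents).** Nothing is imputed, and "the denominator will be the patients with non-missing HbA1c data at Week 24 or Week 48".
- **Model (both documents).** The endpoint will "also be analyzed by a logistic regression model, with logit link function", with treatment and baseline HbA1c as terms.
- **Sensitivity analyses (SAP item 3 only).** The analysis is repeated after censoring efficacy data once patients have "changed the randomized treatment regimen at Week 24 and Week 48, Ancova analyses for row data and LOCF data".

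At the head of the same SAP section stands a general rule: "Missing efficacy values which are HbA1c, FPG, FSBG-based FBG, PPG, BG excursion daily insulin, body weight, SEITQ score will do LOCF". Item 3's no-imputation rule contradicts it for HbA1c, and the SAP does not say which prevails.

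Regimen changes are collected for all participants (Protocol 9.9.1). Insulin treatment and non-insulin glucose-lowering medication are recorded at every visit (Protocol section 2).

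**The concern.** A denominator of patients with an HbA1c suits an endpoint that consists only of HbA1c. In a composite that also requires no switch, no discontinuation and no rescue, one recorded event settles the outcome. Leaving that patient out for want of an HbA1c discards a known result. No text in either document counts such a patient as a non-achiever.

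What is at stake is the level of the reported rate and, if the pattern differs by arm, the comparison. The trial is open label, and Protocol 5.4 places no restriction on switching or augmenting insulin, so regimen changes may well differ between arms.

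The inherited sensitivity analysis raises a separate problem. Removing data after a regimen change removes the very events that define failure, so it cannot show how robust the composite is.

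**Working it through.** **Planning figures.** SAP section 5 assumes 332 evaluable patients per arm and 20% without an evaluable post-baseline HbA1c. 332 / 0.80 = 415 randomised, which reproduces the plan, so 415 − 332 = 83 per arm have no HbA1c. This is a Week 24 figure. The documents give no missing share for Week 48, and no rate or power for endpoint 10.

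**Inputs**

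- m = share without HbA1c: 20% (SAP section 5).
- q = share below 7% among event-free patients: 60%, assumed, and taken as equal with and without HbA1c.
- s = share with a failure event among those with HbA1c: 25%, assumed.
- f = share with a failure event among those without HbA1c: unknown, varied.

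**Level of the rate**

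Planned rate = q(1 − s) = 0.60 × 0.75 = 45.0%, or 149.4 of 332.

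All-randomised rate = [149.4 + 83 × (1 − f) × 0.60] / 415.

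Gap (planned minus all-randomised) = m × q × (f − s).

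| f | All-randomised rate | Gap, points |
|---|---|---|
| 10% | 194.22/415 = 46.8% | −1.8 |
| 25% | 186.75/415 = 45.0% | 0 |
| 35% | 181.77/415 = 43.8% | +1.2 |
| 50% | 174.3/415 = 42.0% | +3.0 |

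At f = 50% the gap runs from 2.0 to 3.75 points for q from 40% to 75%, and from 1.5 to 4.5 points for m from 10% to 30%.

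**Comparison of arms.** Let f differ by arm and hold m, q and s equal. Both planned rates are then 45.0%, so the planned difference is zero. The all-randomised difference is 0.20 × 0.60 × (0.35 − 0.25) = 1.2 points for f of 35% against 25%, and 0.20 × 0.60 × (0.50 − 0.25) = 3.0 points for 50% against 25%. The plan hides that difference. If f is equal in both arms, nothing is hidden.

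**Censoring on raw data.** Suppose 45% of patients who do not change regimen are at goal, there is no rescue, and 10% in one arm against 30% in the other switch or discontinue before the HbA1c (all assumed). The composite is 0.45 × 0.90 = 40.5% against 0.45 × 0.70 = 31.5%, a 9-point difference. After censoring, the changers have no HbA1c and leave the denominator, so the result is 45% against 45%. If a changed regimen also covers intensification and reduced frequency, patients who are not failures under endpoint 10 are removed as well.

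**Three ways to treat patients without HbA1c**

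- *Count known failures but still drop event-free patients without HbA1c.* At f = s = 25% this gives 149.4 / (332 + 83 × 0.25) = 149.4 / 352.75 = 42.4%, against a true 45.0%.
- *Count every patient without HbA1c as a non-achiever.* This gives 149.4 / 415 = 36.0% whatever f is, so it cannot show an arm difference in f. Its error is m × q × (1 − f), which exceeds the plan's whenever 1 − f > |f − s|, that is for f below (1 + 0.25)/2 = 62.5%. With f = s and 15% against 25% missing, it yields 0.45 × 0.85 = 38.25% against 0.45 × 0.75 = 33.75%, a false difference of 4.5 points.
- *Count known failures and impute HbA1c for event-free patients.* If q is the same with and without HbA1c, this targets the all-randomised rate in the table at every f.

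**The case against.** The strongest objection is that few known failures may lack an HbA1c. Switching does not end participation, so many failures will have a scheduled HbA1c and be counted correctly. Early leavers have an HbA1c scheduled at the termination visit, and Protocol 10.3.1 and SAP Appendix 1 use the last value in the window, so that value can count. The planned 20% are dropouts, and dropping out is not a failure event. Early dropouts also have less time to accrue one, since discontinuation requires 30 days or more off insulin. An f below s, where the planned rate is too low, is therefore plausible. All of this stands and limits the size. It does not help a known failure with no HbA1c in the window.

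Two further limits stand. Rescue has no row of its own in the schedule and is left to the investigator, so a rescue failure is known only if it can be derived from the medication records. The ANCOVA wording repeats the sentence that closes item 2 for the continuous endpoints. It looks like a copying slip and touches sensitivity analyses only, because the main model is logistic.

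SAP 8.3.1 offers partial visibility: "Proportion of patients who experience insulin discontinuation, switch, intensification or reduction in frequency during 48 weeks and P value should be in summary statistics". It omits rescue and does not link events to missing HbA1c.

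A reader might infer that the plan always overstates the rate, or that unequal f inflates the false-positive rate. The documents support neither. The sign of the gap depends on f − s, which they do not give. With the other inputs equal, unequal f leaves the planned arms at the same rate, so a difference is masked and none is created.

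**Conclusion.** The point holds, as a minor one. Both documents leave out of endpoint 10 any patient with a recorded failure but no HbA1c, and no other passage repairs this. The documents determine neither size nor direction. Under the assumed inputs the planned 45.0% compares with 46.8% to 42.0% for f from 10% to 50%, with no bias at f = s. A real arm difference of 1.2 to 3.0 points would be masked in the two unequal-f cases. These figures rest on the Week 24 planning share of 20%, the assumed q and s, and equal q with and without HbA1c.

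The inherited raw-data censoring does not test the composite, and ANCOVA is the wrong label for a binary endpoint. Both faults are in the SAP only.

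It would go too far to treat all 83 patients per arm as known failures. That is the extreme f = 100%, giving 36.0%, and the documents describe these patients only as dropouts. The primary analysis, sample size and success criterion are unaffected.

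**What to change.** In SAP 8.2.2, with Protocol 10.3.3.2 aligned on the first two items:

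1. Analyse endpoint 10 on all randomised patients. Classify anyone with a recorded switch, discontinuation or rescue up to the analysis visit, or up to study exit if earlier, as a non-achiever whatever the HbA1c status.
2. In the main analysis, multiply impute HbA1c for event-free patients without it. Use the rule that counts them as non-achievers only as a sensitivity analysis. Do not adopt item 1 while still dropping these patients, because that lowers the rate artificially.
3. Do not apply regimen-change censoring to endpoint 10.
4. Use the stated logistic model in the sensitivity analyses of items 3 and 4.
5. State that item 3's no-imputation rule overrides the general LOCF sentence for the plain below-7% endpoint, and that item 2 of this list governs endpoint 10.

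The cost is some wording, one imputation run, and a written derivation of rescue from medication records that are already collected. No new data are needed, and no clinical rule for rescue is proposed.
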